## Clinical Investigational Plan

### 1.0 Synopsis

Title:	Assessment of the St. Jude Medical Portico™ Re-sheathable Aortic Valve System – Alternative Access
Acronym:	Portico Alternative Access
Purpose:	The purpose of this clinical investigation is to expand the indication of the Portico TF Delivery System and obtain approval of the Alternative Access Delivery System to place a Portico transcatheter aortic valve through an alternative access site, specifically subclavian/axillary or transaortic (TAo) in subjects with symptomatic severe native aortic stenosis who are considered high surgical risk.
Endpoints:	
Primary Endpoint: The study will have a single primary safety endpoint of major vascular complications through 30 days, as defined by the Valve Academic Research Consortium^1 (VARC-2) for each access arm of the study.
 
Secondary Endpoints for each access arm of the study:
 
 
The event rates at 30 days of the following: 
 
All-cause mortality
 
Cardiovascular mortality
 
Disabling stroke
 
Non-disabling stroke
 
Life-threatening bleeding requiring transfusion
 
Acute kidney injury requiring dialysis
 
Composite of 
 
Periprocedural encephalopathy
 
all stroke
 
all TIA
 
 
 
 
 
The event rates at 1 year of the following: 
 
All-cause mortality
 
Cardiovascular mortality
 
Disabling stroke
 
Moderate and severe aortic regurgitation
 
 
 
Improvement from baseline as compared to 30 days by: 
 
NYHA Functional Classification
 
Six minute walk test
 
Effective Orifice Area (EOA)
 
 
 
Acute device success defined as: 
 
Absence of procedural mortality
 
Correct positioning of a single prosthetic heart valve into the proper anatomical location
 
Intended performance of the prosthetic heart valve 
 
mean aortic valve gradient <20 mmHg
 
peak velocity <3 m/s
 
no moderate or severe prosthetic valve regurgitation
 
 
 
 
 
 
In addition successful access, delivery and deployment of the valve and retrieval of the delivery system will be collected.

**Clinical Investigational Plan**

Design:	
This is a multicenter prospective, non-randomized, 2-arm investigational study without concurrent or matched controls, designed to assess the use of the Portico TF or Alternative Access Delivery System to place a transcatheter aortic valve through an alternative access site, specifically subclavian/axillary and TAO.
 
A minimum of 45 subjects will undergo transcatheter aortic valve replacement (independent of valve size) using the Portico TF or Alternative Access Delivery System in each study access arm (subclavian/axillary and TAO). A minimum of 45 implants will be accessed via the subclavian/axillary access site and a minimum of 45 implants will be accessed via the TAO access site. A maximum of 12 investigational sites with prior alternative access technique experience in Europe will be trained to participate in the study. Enrollment is anticipated to be completed approximately 8 months from the date of first enrollment. Data will be collected at pre-procedure, peri-procedure and at discharge as well as at 30 days, 6 months and 1 year post implantation. All active subjects will be followed for 1 year.
 
Data from other prospective Portico clinical trials with ALT access in similar patient populations outside of Europe may be included in the analysis and support the submission for CE Mark. CE Mark will be submitted for each access route after implantation and 30 day follow up are completed.
 
Although the study will not test a hypothesis, the primary endpoint event rate for each cohort will be presented within the context of the range of rates reported for alternative access delivery of transcatheter valves in the literature.

Devices used:	
The devices to be used in this study are the Portico delivery systems which are available in two different lengths, 110 and 65cm. Both of these devices are considered investigational for alternative access use. The 110cm delivery system is already CE marked for Transfemoral access. This study will also use the CE marked Transfemoral/Alternative Access Loading systems (18 or 19F) and Portico valves available in 23, 25, 27 and 29mm sizes.

Study Population	
A patient becomes a subject once he/she has been fully informed about the study, has agreed to participate, signed & dated the consent.

Inclusion/Exclusion Criteria	
Inclusion Criteria
 

1. Subject has provided written informed consent prior to uploading CT scan to core lab.

2. Subject is <math>\geq 18</math> years of age or legal age in host country.

3. Subject's aortic annulus diameter meets the range indicated in the Instructions for Use as measured by multislice CT conducted within 180 days prior to the index procedure.

4. Subject has senile degenerative aortic stenosis seen by echocardiography within 90 days of index procedure as measured by one of the following:

**Clinical Investigational Plan**

- Mean gradient  $\geq 40$  mmHg
  - Peak velocity  $\geq 4.0$  m/s
  - Doppler Velocity Index  $< 0.25$
  - Aortic valve area (AVA) of  $< 1.0 \text{ cm}^2$  or indexed EOA  $< 0.6 \text{ cm}^2/\text{m}^2$ .
5. Subject has symptomatic aortic stenosis as demonstrated by NYHA Functional Classification of Class II, or greater or other symptoms of aortic stenosis (e.g. syncope).
  6. Subject is deemed high operable risk and preferred TAVI delivery route is alternate access (subclavian/axillary or direct aortic) per the medical opinion of the center's heart team and confirmed by SSC.
- High risk is defined as an STS mortality  $\geq 8\%$  or documented heart team agreement  $\geq$  high risk for SAVR due to frailty or co-morbidities

**Exclusion Criteria**

1. Subject is unwilling or unable to comply with all study-required follow-up evaluations.
2. Subject has a documented history of a cerebral vascular accident (CVA) or transient ischemic attack (TIA) within 6 months (less than or equal to 180 days) prior to the index procedure.
3. Subject has carotid artery disease requiring intervention.
4. Subject has evidence of a myocardial infarction (MI) within 30 days prior to patient index procedure.
5. Subject has a native aortic valve that is congenitally unicuspid, bicuspid, quadricuspid or non-calcified as seen by echocardiography.
6. Subject has severe mitral valvular regurgitation.
7. Subject has severe mitral stenosis.
8. Subject has a pre-existing prosthetic cardiac device, valve, or prosthetic ring in any position.
9. Subject refuses any blood product transfusion.
10. Subject has resting left ventricular ejection fraction (LVEF) less than 20%.
11. Subject has documented, untreated symptomatic coronary artery disease (CAD) requiring revascularization.
12. Subject has had a percutaneous interventional or other invasive cardiovascular or peripheral vascular procedure less than or equal to 14 days prior to index procedure.
13. Subject has severe basal septal hypertrophy that would interfere with transcatheter aortic valve placement.

**Clinical Investigational Plan**

14. Subject has a history of, or is currently diagnosed with, endocarditis.
15. There is imaging evidence of intracardiac mass, thrombus, or vegetation.
16. Subject is considered hemodynamically unstable (requiring inotropic support or mechanical heart assistance).
17. Subject is in acute pulmonary edema or requiring intravenous diuretic therapy to stabilize heart failure.
18. Subject with severe pulmonary disease as determined by STS score.
19. Subject is on chronic oral steroid therapy.
20. Subject has a documented hypersensitivity or contraindication to anticoagulant or antiplatelet medication.
21. Subject has renal insufficiency as evidenced by a serum creatinine greater than 3.0 mg/dL (265.5  $\mu$ mol/L) or end-stage renal disease requiring chronic dialysis.
22. Subject has morbid obesity defined as a BMI greater than or equal to 40.
23. Subject has ongoing infection or sepsis.
24. Subject has uncontrolled blood dyscrasias as defined: leukopenia ( $WBC < 3000 \text{ mm}^3$ ), acute anemia ( $Hb < 9 \text{ g/dL}$ ), thrombocytopenia (platelet count  $< 50,000 \text{ cells/mm}^3$ ).
25. Anatomy falling outside the recommended values in the IFU, unless specifically approved by the Subject Selection Committee.
26. Subject has an active peptic ulcer or has had gastrointestinal (GI) bleeding within 90 days prior to the index procedure.
27. Subject is currently participating in another investigational drug or device study, unless approved by the Sponsor.
28. Subject has/had emergency surgery for any reason within 30 days of the index procedure.
29. Subject has a life expectancy less than 1 year.
30. Subject has other medical, social or psychological conditions that, in the opinion of the site Heart Team or the Subject Selection Committee, preclude the subject from study participation.
31. Subject is diagnosed with a state of dementia which would fundamentally complicate rehabilitation from the procedure or compliance with follow-up visits.
32. Subject has a documented allergy to contrast media that cannot adequately be treated, nitinol alloys, porcine tissue, or bovine tissue.

**Clinical Investigational Plan**

	
33. Significant aortic disease including abdominal aortic or thoracic aneurysm defined as maximal luminal diameter 5cm or greater
 
34. Subjects with severe pulmonary hypertension and severe RV dysfunction
 
35. Subjects with hypertrophic cardiomyopathy
 
Transaortic Subject Cohort Specific Exclusion Criteria
 

1. Subject has a chest condition (anatomical or otherwise) that prevents TAO access.

2. Subject has pre-existing patent RIMA graft that would preclude access.

3. Subject has a porcelain aorta, defined as an extensive circumferential calcification of the ascending aorta that would complicate TAO access.

 
Subclavian/Axillary Subject Cohort Specific Exclusion Criteria
 

1. Subject's access vessel (subclavian/axillary) diameter will not allow for introduction of the 18/19 Fr delivery system.

2. Subject's subclavian/axillary arteries have severe calcification and/or tortuosity.

3. Subject has a history of LIMA/RIMA graft that would preclude access

Data Collection	
Data will be collected pre-procedure, peri-procedure, and discharge as well as 30 days, 6 months and 1 year post implantation.
 
A Clinical Events Committee (CEC) will adjudicate the relatedness of endpoint events with respect to the procedure, delivery system, valve and by event type according to the VARC-2 endpoint definitions document. CEC adjudications will be used when assessing and reporting study results.

## Clinical Investigational Plan

### 2.0 Background and Justification for Clinical Study

Aortic Stenosis (AS) is currently the most common valvular disease in the Western population and its prevalence tends to increase with age, being present in 4.6% of adults  $\geq 75$  years. Replacement of the aortic valve remains an effective treatment of severe AS. There was a near doubling of surgical aortic valve replacements (AVRs) over a 10-year period (1995-2004) and the need for AVR is projected to escalate as the population grows older due to the increase in life expectancy.

The average life expectancy of patients with severe, symptomatic AS is 2-3 years from the onset of symptoms with a significant risk of sudden death. Symptomatic aortic stenosis is an accepted indication for surgery, in which valve replacement can both reduce symptoms and extend life. Despite this, many patients with severe aortic stenosis do not undergo surgery because of excessive risk, advanced age, or preference. Prognosis with medical management is poor and prior to TAVR, percutaneous alternatives to surgery have been limited to balloon valvuloplasty with palliation that is modest and short-lived.

Many patients with severe AS are considered high surgical risk and do not undergo AVR due to severe comorbidities. Because of the limited therapeutic options in patients deemed at high surgical risk, there was interest in the development of a less invasive method to restore valve function.

With technological advancements, an alternative to surgical AVR, known as TAVR (Transcatheter Aortic Valve Replacement) and TAVI (Transcatheter Aortic Valve Implantation) has been under active investigation and proven safe and effective by a number of groups. This concept was first demonstrated by Andersen et al in 1992, who delivered a porcine bioprosthesis attached to a wire-based stent at various aortic sites with satisfactory hemodynamic results. In 2002, Cribier et al, reported the first successful human TAVI for the treatment of severe symptomatic aortic stenosis. Several single-center trials followed which demonstrated that this new approach was feasible for the treatment of severe aortic stenosis in patients who were inoperable or at a very high risk for standard surgical aortic valve replacement.

The safety and effectiveness of TAVI is now confirmed with the recent published results of the randomized, controlled PARTNER trial, CoreValve IDE which demonstrated the noninferiority of TAVI as compared to conventional AVR in high risk patients.

The first two devices commercially available were the Medtronic CoreValve™ (Medtronic Inc., Minneapolis, Minnesota), and the Edwards Sapien™ valve (Edwards Lifesciences Corporation, Irvine, CA) which received CE Mark in 2007 for transarterial implantation. In addition, the Edwards Sapien prosthesis received CE Mark for transapical implantation in December 2007. The Edwards Sapien XT™ valve (Edwards Lifesciences Corporation, Irvine, CA) received CE Mark in 2010 for transarterial and transapical implantation. In October 2011, two additional valves received CE Mark: the JenaValve™ valve (JenaValve Technology München, Germany) and the Symetis Acurate TA™ system (Symetis, Ecublens, Switzerland). Both valves are designed for a percutaneous aortic valve implantation via a transapical route.

Transcatheter aortic valve replacement was originally described through an antegrade transseptal route by Cribier and colleagues in 2002. Because of the complexity of the procedure and risks associated with crossing the mitral valve, this approach has been abandoned in favor of more reproducible alternatives, primarily the transfemoral (TF) route.

## Clinical Investigational Plan

Typically, TF access is the initial default strategy unless the vascular anatomy conveys a prohibitive risk due to vessel tortuosity, small caliber, or heavy calcification.

Although the TF route is the least invasive, it may not be feasible in every patient. General (absolute and relative) contraindications to the TF approach include severely calcified or tortuous iliac arteries; an iliac artery diameter of < 6 mm to < 9 mm (depending on the type of device used); previous aortofemoral bypass grafts; severely angulated aorta or atherosclerotic aortic arch; transverse ascending arch (for balloon-expandable devices); and aortic aneurysm with extensive mural thrombus and coarctation of the aorta. In a recent evaluation by Kurra et. al. of 100 patients undergoing TAVR screening, 35% of patients had at least one criterion of unsuitable iliofemoral anatomy, including 27 patients with small minimal luminal diameter (<8 mm), 12 patients with severe circumferential calcification at the iliac bifurcation (>60%), and 4 with severe angulation of the iliac arteries (<90°).

The decision of using one delivery approach versus another is typically based upon a multidisciplinary team's consensus, comprising the expertise of interventional cardiologists, imaging cardiologists, cardiac surgeons, and cardiac anesthetists - following a careful evaluation of the patient. Even though the experience and skills of the operators have improved and new technologies have become available since the initial TAVI experiences, patient selection remains a key element in the TAVI outcome. Selection criteria have a crucial influence on complication rates and clinical outcomes after TAVI.

Subclavian/axillary and Transaortic (TAo) access have been introduced as alternative routes in patients with difficult transfemoral access for implantation of a transcatheter heart valve. Compared to the TF approach, subclavian/axillary and TAo access provides a less remote access point to the aortic valve. This shorter distance also reduces bending stress on the delivery system through multiple vasculature points potentially improving steerability and placement control of the transcatheter aortic valve.

The subclavian/axillary approach is preferably performed via the left subclavian artery. Hence, a patent left internal mammary artery (LIMA) graft is a relative contraindication for TAVR from the left side. In these patients, the right subclavian artery can be used; however, it may be challenging to achieve the correct angulation of the transcatheter aortic valve during positioning. The presence of a permanent pacemaker in the left pectoral region is not an absolute contraindication.

Transaortic (TAo) approach, also known as "direct aortic" access, provides proximate, direct access to the aortic annulus allowing for precise manipulation of both the delivery system and transcatheter heart valve. This is important in cases where the implantation with other approaches (e.g., TF, TA) may be difficult such as cases with a vertical valve orientation, a horizontal ascending aorta, or where the native valve is at the upper limit of the size.

TAo approaches are either through a ministernotomy or through a mini-right thoracotomy. In a ministernotomy, a limited skin incision (5 cm) is made starting just below the sternal notch. A partial upper sternotomy (J-shape) is performed through the second or third right intercostal space. This exposes the upper portion of the ascending aorta for direct cannulation. A ministernotomy is preferred in obese patients, patients with an ascending aorta in the mid-line/to the left or a short ascending aorta, and in patients with poor respiratory reserve because the pleura remains intact, and it has less effect on the respiratory dynamics. This approach can also be used in patients with previous coronary artery bypass grafting and a patent LIMA graft provided that the LIMA graft is not in the mid-line and the innominate vein and aorta are not in close proximity to the sternum.

## Clinical Investigational Plan

The use of each of these alternate access approaches has been demonstrated to be a safe and effective means of delivering transcatheter aortic valves as evidenced by the approved products mentioned above and thus increases the number of patients who can be treated successfully and can ultimately benefit from transcatheter aortic valve replacement.

### 3.0 Device under Investigation

#### 3.1 Portico TF and ALT Delivery System

The study will use the CE Marked Portico™ transcatheter valves available in 23, 25, 27, and 29mm sizes. The devices under investigation are the Portico TF (110cm) Delivery System and the Alternative Access (65cm) Delivery System which both come in 18 Fr or 19 Fr diameter. Both delivery systems are over-the-wire, (0.035"-compatible). The outer diameter of the delivery systems is 18 Fr and 19 Fr at the distal end and 13 Fr at the proximal end.

The delivery system design facilitates gradual, controlled deployment of the valve. If needed, the valve may be re-sheathed and repositioned up to 2 times, provided the valve has not been >80% deployed.

The valve is deployed annulus end first, from the distal end of the delivery system. The distal end of the delivery system includes an atraumatic radiopaque tip to guide the delivery system and facilitate visualization. The protective sheath covers and maintains the valve in the collapsed position. The protective sheath features a marker band that provides a reference point used to determine the extent of the valve deployment. The protective sheath may be advanced or retracted to facilitate valve loading and deployment. When the protective sheath is retracted, the inner shaft is exposed. The valve is loaded onto the inner shaft. Retainer tabs on the valve lock into a retainer receptacle that is mounted on the inner shaft. The inner shaft also features a radiopaque inner shaft marker band that provides a reference point used to align the valve in the native annulus.

[figure not shown]

Figure 1: Portico Delivery System

**Clinical Investigational Plan****Table 1: Regulatory Status of Devices**

Device Component	Model/Type	Investigational or Market Released
110cm Delivery System	18F TF Delivery System	Market Released*
110cm Delivery System	19F TF Delivery System	Market Released*
65cm Delivery System	18F ALT Delivery System	Investigational
65cm Delivery System	19F ALT Delivery System	Investigational
Loading System	18F Transfemoral/Alternative Access Loading System	Market Released
Loading System	19F Transfemoral/Alternative Access Loading System	Market Released
Valve	PRT-23	Market Released
Valve	PRT-25	Market Released
Valve	PRT-27	Market Released
Valve	PRT-29	Market Released

\*Will be investigational when used for alternative access delivery

**3.2 Device Handling and Storage**

Abbott requires all investigational products be stored, according to the labeling, in a secure area to prevent unauthorized access or use. This will prevent non-investigational use of products that are provided only for use in this study.

**3.3 Device Accountability**

An Abbott representative will notify the sites of activation. Investigational product shall be shipped after the site is activated and shipping authorization is complete.

The Principal Investigator or an authorized designee must maintain a device accountability log documenting the date of receipt, the identification of each investigational device (batch number, lot number or unique code), the subject identification, the date of use, the expiration date and final disposition.

Storage locations for the investigational use only labeled devices will be locked with access restricted only to Investigators and authorized research personnel.

St. Jude Medical must also maintain device accountability documenting all shipments and returns of investigational labeled devices.

## Clinical Investigational Plan

### 4.0 Study Design

#### 4.1 Purpose

The purpose of this clinical investigation is to expand the indication of the Portico TF Delivery System and obtain approval of the Alternative Access Delivery System to place a transcatheter aortic valve through an alternative access site, specifically subclavian/axillary or TAO in subjects with symptomatic severe native aortic stenosis who are considered high surgical risk.

#### 4.2 Study Design and Scope

This is a multicenter prospective, non-randomized, 2-arm investigational study without concurrent or matched controls, designed to assess the use of the Portico TF or Alternative Access Delivery System to place a Portico transcatheter aortic valve through an alternative access site, specifically subclavian/axillary or TAO.

A minimum of 45 subjects will undergo transcatheter aortic valve replacement (independent of valve size) via the Portico TF or Alternative Access Delivery System in each arm. A minimum of 45 implants will be accessed via the subclavian/axillary access site arm of the study and a minimum of 45 implants will be accessed via the TAO access site arm of the study. A maximum of 12 investigational sites with prior alternative access technique experience in Europe and will be trained to participate in the study. Enrollment is anticipated to be completed approximately 8 months from the date of first enrollment. Data will be collected at pre-procedure, peri-procedure and at discharge as well as at 30 days, 6 months and 1 year post implantation. All active subjects will be followed for 1 year.

Data from other prospective clinical trials of ALT access in similar patient populations outside of Europe may be included in the analysis and support the submission for CE Mark. CE Mark will be submitted for each access route after implantation and 30 day follow up are completed.

Although the study will not test a hypothesis, the primary endpoint event rate for each cohort will be presented within the context of the range of rates reported for alternative access delivery of transcatheter valves in the literature.

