##### 6.2.1.1 Analysis Methodology

The proportion of subjects experiencing a primary safety endpoint through 30 days (less than or equal to 30 days) post implant will be estimated as the number of subjects who experience the safety endpoint divided by the total number of subjects in the analysis population (see Section 6.2.1.2). The 95% upper confidence limit for the proportion of subjects experiencing a primary safety endpoint will be calculated using the exact binomial method.

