##### 6.2.1.2 Analysis Population

All subjects who have received a Patient Information Sheet, and signed an Informed Consent Form and Data Protection Form will be considered enrolled in the study. However, the analysis population will be based on subjects who have provided signed Informed Consent Form and Data Protection Form and had the SJM TAVI delivery system enter his/her body. The anticipated dropout rate for this study population is expected to be low, as part of the selection criteria is subject compliance with all follow-up visits. Subjects that withdraw from the investigation or are lost to follow-up will not be replaced in the analysis dataset.

It is anticipated that there may be subjects who are enrolled in the study but are not included in the analysis population. There may be subjects who gave consent to participate in the study but did not satisfy the baseline inclusion exclusion criteria, these are considered screen failures. There may also be subjects who have enrolled in the study and started the procedure, but do not have the SJM TAVI delivery system enter his/her body and are procedural exclusions due to their anatomy, circumstances related to the procedure, or physician judgment; these are considered to be procedural exclusion subjects. Screen failure subjects and procedurally excluded subjects will not be part of the analysis population.

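### The synopsis and section 4.2 disagree on whether outside-trial data must be Portico, and neither says whether such data may enter a route's primary rate

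*Combined protocol and SAP*

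**What the plan says.** Two places in the current plan allow data from other trials into the analysis.

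- **Synopsis, Design:** "Data from other prospective Portico clinical trials with ALT access in similar patient populations outside of Europe may be included in the analysis".
- **Section 4.2:** "Data from other prospective clinical trials of ALT access in similar patient populations outside of Europe may be included in the analysis". The word Portico is absent.

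Both are permissive, and both tie the data to the CE Mark file: they "may be included in the analysis and support the submission for CE Mark". Neither names a trial, a number of subjects, a decision date, a method of combination or an adjudication process.

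The statistical section does not mention outside data. Section 6.2.1.1 takes the primary rate over the section 6.2.1.2 population. In that section "the analysis population will be based on subjects who have provided signed Informed Consent Form and Data Protection Form" and who "had the SJM TAVI delivery system enter his/her body". Section 6.5 locks each route's CE Mark dataset once 45 subjects have reached, or passed, the 30-day visit. Section 4.2 also sets a floor within this study: "A minimum of 45 implants will be accessed via the subclavian/axillary access site arm of the study", and likewise "a minimum of 45 implants will be accessed via the TAO access site arm of the study".

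**The concern.** The study has no control group and no formal hypothesis. Its main result is one 30-day major vascular complication rate per route, with an exact 95% upper limit, read against a literature range of 5-23.3% (section 6.6). Who is in the numerator and denominator is therefore most of what there is to specify.

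The design section permits outside subjects in the analysis. The statistical section defines the analysis without them. Nothing says which governs. The arms are not masked, and the sponsor analyses the data (section 10.0), so event counts can be known before anyone decides whether to use the permission. A choice made then, even in good faith, tends to move the reported rate in one direction.

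Comparability is a second issue. This study's subjects are reviewed by its Subject Selection Committee (section 7.2), and its results rest on its own CEC's adjudications (synopsis, Data Collection). The plan does not require either for outside subjects.

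**Working it through.** **1. The texts side by side**

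| Question | Synopsis | Section 4.2 | Sections 6.2.1.1, 6.2.1.2, 6.5 |
|---|---|---|---|
| Outside data allowed? | Yes, optional | Yes, optional | Not mentioned |
| Portico only? | Yes | Not stated | Population requires the SJM delivery system |
| Which analysis? | Not stated | Not stated | Primary rate on the 6.2.1.2 population |
| Which trials, chosen when? | Not stated | Not stated | Lock at 45 subjects per route |

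**2. The plan's own figure**

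Inputs from section 6.3: rate 5.9%, n = 45, so x = 0.059 × 45 = 2.655. The exact 90% limits are beta quantiles:
- lower: 5% quantile of Beta(x, n − x + 1) = Beta(2.655, 43.345), which is 1.45%
- upper: 95% quantile of Beta(x + 1, n − x) = Beta(3.655, 42.345), which is 15.32%

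Both match the plan. The same upper-limit formula is used below.

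**3. What adding outside subjects can do to one arm**

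The plan gives no outside counts, so those here are assumed. The range of 5-23.3% is from section 6.6. The pooled rate is (k + y)/(45 + m), for k events in the arm and y events in m outside subjects.

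| Data | Rate | Exact 95% upper limit | Rate inside 5-23.3%? |
|---|---|---|---|
| 11/45, this study alone | 24.4% | 37.2% | No |
| plus 1/20: 12/65 | 18.5% | 28.2% | Yes |
| plus 2/45: 13/90 | 14.4% | 22.0% | Yes |

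With 45 outside subjects and anything from 0 to 9 outside events, the pooled rate runs from 11/90 = 12.2% to 20/90 = 22.2%, inside the range throughout. The example shows the mechanism and is not a forecast: at a true rate of 11.9%, the binomial chance of 11 or more events in 45 is about 1.5%.

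**4. Bias from choosing after seeing both**

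Assume a true rate of 11.9% (the pooled literature estimate in section 6.3) in both sources, with K ~ Bin(45, 0.119) and Y ~ Bin(m, 0.119) independent. If the lower rate is reported, its expectation is the sum over all k and y of P(K = k) × P(Y = y) × min{k/45, (k + y)/(45 + m)}.
- m = 20: 10.8%
- m = 45: 10.6%

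Against a truth of 11.9%, that is a downward bias of 1.1 and 1.3 percentage points. It comes from the choice alone, because both sources have the same true rate.

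Under the same assumptions, the chance that the upper limit is at or below 23.3% rises from 55% alone to 78% (m = 20) or 90% (m = 45). Most of that rise comes from the larger sample: always pooling gives 76% and 89%. So the bias in the rate is the better measure of the problem.

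**The case against.** **Some readers would infer that the primary rate need not come from this study or from this device.** The text does not support that. Section 4.2 requires at least 45 implants per route within this study, section 6.5 locks on 45 subjects per route, and section 6.2.1.2 requires the SJM delivery system. Outside data could be added to the study's data but could not replace them. Non-Portico data would contradict both the synopsis and section 6.2.1.2. Section 4.2 itself opens by describing placement of a Portico valve, so the missing word may be a drafting slip. It still needs correcting.

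**A reader might also infer that the plan provides for adding data once results are known.** It says nothing on timing. The defensible statement is that it does not prevent this.

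**A less extreme arm may look like a better example.** At 6/45 the upper limit is 24.6%, above 23.3%. But section 6.6 applies the range to the primary endpoint result, and 13.3% is already inside. Section 6.3 sets an upper limit against the range only as a planning remark.

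**There is no hypothesis or alpha, so no test is inflated, and section 6.9 requires departures from the statistical plan to be documented.** The first part is correct. The second helps only if adding outside subjects counts as a departure. Because section 4.2 permits it, that depends on which section governs, and the plan does not say.

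**Pooling same-device data can be legitimate with 45 subjects per arm.** Agreed, if it is specified in advance and labelled as supportive. The documents also do not say how outside trials screen or adjudicate, so non-comparability is unaddressed rather than shown.

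**Conclusion.** The point holds as an unresolved conflict with a practical consequence. The synopsis and section 4.2 differ on the Portico limit. Neither is reconciled with the sections that define the primary rate, so a reader cannot tell whether a route's rate and upper limit may include outside subjects.

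Used at discretion with the result in view, the permission could bring an arm at 24.4% inside the 5-23.3% range. It would also lower the expected reported rate from 11.9% to between 10.6% and 10.8%. These sizes rest on assumed outside samples of 20 or 45 subjects, on assumed outside event counts in the first case, and on equal true rates with the lower result always reported in the second. They show what the wording leaves open. They do not show that the sponsor intends it.

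**What to change.** - In the synopsis, section 4.2 and section 6.2, state that the primary and secondary endpoint analyses for each route, including the exact 95% upper limit, use only the section 6.2.1.2 population treated under this CIP.
- Restore Portico in section 4.2 so that it agrees with the synopsis.
- Present any outside Portico data, alone or pooled with this study, only as a separately labelled supportive analysis. Fix the trials, the VARC-2 definition, the adjudication and the method of combination before the 30-day lock.

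The cost is wording. The planned 45 per route and the 15.32% planning limit do not change. The sponsor gives up optional precision in the headline rate but can still submit the outside data beside it.
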